2.3 Other Objectives

- 1. To assess the economic impact of the intervention by comparing medical costs between treatment arms, inclusive of the cost for rehabilitation therapy, relative to its associated changes in health outcomes.
- 2. To estimate the proportion of the reduction in rehospitalizations explained by the intervention's effect on the SPPB score.
- 3. To examine the effect of the intervention on these exploratory endpoints:

- 1. Change in the Kansas City Cardiomyopathy Questionnaire (KCCQ) total score and physical component score at 3 months
- 2. Change in 6-minute walk distance (6MWD) at 3 months
- 3. Change in component scores of the SPPB at 3 months
- 4. Change in the 12-item short form health survey (SF-12), depression, and cognition measures at 3 months
- 5. Change in frailty status at 3 months
- 6. All-cause rehospitalizations at 1 month and 3 months
- 7. All-cause rehospitalizations 6 months from the date of randomization
- 8. All-cause combined rehospitalization and death at 6 months
- 9. Global rank endpoint of SPPB score + all-cause rehospitalization + death
- 10. Heart failure (HF)-specific rehospitalizations
- 11. Cardiovascular events
- 12. All-cause rehospitalization days
- 13. Total hospitalization days post-randomization
- 14. Total facility-free days alive
- 15. Deaths
- 16. Falls
- 17. Change in biomarkers at 3 months
- 18. Blood-based bioenergetics profiling.

3. Background

ADHF is the leading cause of hospitalization in persons > 60 years in the United States. Hospitalized ADHF is associated with severely reduced health-related quality of life (QOL), persistently high rehospitalization rates,(1) markedly increased mortality, and costs over \$39 billion per year.(2) Current HF management guidelines, even when perfectly adhered to, have had only modest impact on ADHF outcomes, particularly rehospitalizations in the older population.(1;3-5) Furthermore, several recent trials of new interventions to improve ADHF outcomes, such as telemonitoring,(6;7) alternative diuretic regimens,(8-11) novel agents(11;12) and biomarker guidance have been negative.(9;13) This suggests outcomes in older ADHF patients may be driven partly by mechanisms that are not addressed by current approaches.

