Multiple lines of emerging evidence suggest that severely reduced physical function and frailty strongly contribute to adverse outcomes in older patients with hospitalized ADHF (14) We and others have shown that even when stable with compensated cardiovascular function, older patients with chronic HF have particularly severe impairments in physical function (14-16) due to the combined effects of aging, cardiovascular dysfunction, and impaired skeletal muscle function.(17-27) As patients with chronic HF transition to ADHF, physical function worsens markedly both because of HF decompensation and accelerated physical deconditioning.(19;28;29) This is further exacerbated by the hospital processes, including forced bed rest which can markedly accelerate physical dysfunction.(30-36) We and others have shown that after resolution of the acute HF symptoms and congestion, older ADHF patients continue to have marked impairments in physical function, including strength, balance, mobility and endurance, and that most patients meet formal definitions of frailty.(28;29;37-39) Furthermore, these deficits persist and some patients never recover baseline function.(14;33;40-43) This occurs during the most vulnerable, high risk period for rehospitalization and adverse outcomes - up to 6 months post discharge. (44;45) We hypothesize that this physical frailty predisposes patients to adverse outcomes and that this cascade of events contributes to the persistently high rates of adverse outcomes, including rehospitalization, in older HF patients.(4;16;28;29;37;38;41;42;45-47)

The typical older ADHF patient has > 5 comorbidities(14;48;49) and these contribute to impaired physical function(50) and subsequent adverse outcomes.(4;14;28;47;49;51-56) Impaired physical function and frequent non-cardiac comorbidities may explain the unexpected finding from multiple studies that > 50% of rehospitalizations in older ADHF patients are due to non-cardiac events rather than recurrent ADHF.(4;14;40;48;49;57-59)

In our published model,(14) we have identified 5 factors that contribute to severely impaired physical function and subsequent events in older ADHF patients: aging-related changes, the primary HF disease, deconditioning, multiple comorbidities, and iatrogenesis. Our data and others' from studies in other medical conditions common in older patients support that targeted physical function interventions can improve impairments related to each of these factors.(21;60-67)

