7.2 Rehabilitation Intervention Group

7.2.1 REHAB-HF Rehabilitation Intervention Overview

The multi-domain rehabilitation intervention for this study is a novel integration of rehabilitation therapies developed specifically for older heart failure patients who have been hospitalized for ADHF; a population characterized by heterogeneity in mobility status, multiple co-morbid conditions, and high rates of frailty.(48;50;83-85) The goal of the intervention is to increase endurance, mobility, strength, and balance utilizing reproducible targeted exercises administered by a multi-disciplinary team with specific milestones for progression.

This is a transitional intervention which begins during the acute hospitalization and continues for 12 weeks after discharge in the outpatient setting. The intervention will be administered once daily in the hospital and 3 days per week in the outpatient setting. Each session will include 3 stages: 1) warm-up (seated core exercises, 2-3 minutes light walking if able, and stretching exercises), 2) rehabilitation/training, and 3) cool-down (stretching exercises). The rehabilitation/training portion of each session will include exercises tailored based on participant performance in each of 4 domains: endurance, mobility, strength, and balance.

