7.3 Intercurrent Illness and Interruption to Study Intervention

Interruptions to the study intervention, including illness and hospitalization, are anticipated. Although this is an intention-to-treat protocol, to help ensure each participant has a reasonable opportunity to complete the study intervention (defined as completing at least 30 outpatient sessions) and that the physical performance outcome measures reflect the intended intervention of this study, limited extensions of the study intervention are included in the study protocol. Participants who suffer an illness, hospitalization or other complications that interferes with participating in the study intervention will resume the intervention once medically stable. Participants will have up to 4 additional weeks beyond the initially planned 12 weeks to attempt to complete the multi-domain intervention.

In addition, if a participant is acutely ill or hospitalized within 2 weeks of the anticipated date of the final 3-month visit, the visit will be delayed for up to 2 weeks to allow for up to 6 additional rehabilitation and exercise sessions. Similarly, the final 3-month visit for those in the attention control arm will also be delayed for up to 2 weeks in the event of acute illness or hospitalization within 2 weeks of the date of the visit.

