9.1 Follow up schedule

All baseline measures (see Table 2) will be collected during the index hospitalization. Follow up visits will occur 4 weeks ± 3 days and 12 weeks ± 10 days (unless intervention is extended, see section 7.3) from the day of discharge from the index hospitalization. These visits will include a brief history and physical and collection of study measures (see Table 2). Historical information will include heart failure symptoms, NYHA class, current medications, the results of any intervening cardiac studies (echocardiogram, stress tests, etc.), and the occurrence of any clinical events. The focused physical examination will include evaluation of the lungs, heart, and periphery. During these visits, the participants will also complete health status and quality of life measures as well as follow-up measures of physical function as detailed in Table 2 below. To promote retention, all participants will receive in-person contact within the first 2 weeks following discharge, achieved through intervention sessions, home visit, usual care clinic visit, or a scheduled clinic visit. In addition to the follow up visits, participants will receive a scheduled phone call at the end of months 2, 4, 5, and 6 to evaluate clinical status and for follow-up on adherence to the maintenance phase. Additional telephone contact will be made with the attention control group participants (see section 7.1). Telephone contact will also be maintained with participants unable or unwilling to attend the clinic visits. In some instances, participants unable to attend these visits may receive a home visit to collect important end points.

Table 2: Collection of Outcome Measures

	Index Hospitalization (Baseline)	1 Month (Visit)	2 Months (phone call)	3 Months (Visit)	4, 5, & 6 Months (phone call)
6MWT	X	X		X	
SPPB	X	X		X	
Grip	X	Х		Х	
Biomarkers	X			X	
Bioenergetic Profiling	Х			Х	

KCCQ	X	Х		Х	
SF-12	Х	Х		Х	
EQ-5D-5L	Х	X		X	X (6M only)
GDS-15	Х			Х	
LOT	Х			Х	
MoCA	Х			Х	
Clinical	Х	Х	Х	Х	Х
Events	^	^	^	^	^
Medications	Х	Х	Х	Х	Х
Review	Λ	^		X	^
Medical					
Resource		X	X	X	X
Use					

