10.1.1 SPPB

The SPPB was chosen as the primary outcome because: 1) physical function is an independently important outcome in older persons; 2) the SPPB is a well-accepted, reliable. validated measure of physical function in the older population, (89) and is safe and feasible in clinic, home, and hospital settings, (90) including hospitalized older ADHF patients HF; (28;29;37) 3) the SPPB score is highly predictive of important clinical outcomes, including disability, hospitalization, nursing home admission, and death; (89;91-94) 4) it is sensitive to change in health status(95) and responsive to exercise training;(65;67;96;97) 5) interventions that improve SPPB also improve clinical events, providing independent confirmation of validity; (98;99) 6) the SPPB is a key outcome in LIFE, the largest NIA-funded physical function intervention trial; 7) in our pilot study, the improvement in SPPB explained 90% of the improvement in rehospitalizations, providing a mechanistic link; and 8) the SPPB is standardized, simple, and relatively brief (<10 minutes). The SPPB measures physical function using 3 components: usual gait speed over 4 meters, time to complete 5 chair rises, and standing balance with progressively narrow base of support. Each component is scored on a 0-4 scale and summed for an overall score range of 0-12. Each component of the SPPB is independently associated with important outcomes including mortality.(100:100) Gait speed is associated with survival at increments of 0.1 m/s in community-dwelling adults(101) and is associated with survival in hospitalized older adults with coronary disease.(102)

10.1.2 6MWD

The 6MWD test is a well-established outcome measure in HF. It is valid and reproducible in patients with a wide range of physical function, predicts clinical events, and responds to interventions.(103-106) We showed that it is as predictive of clinical events as exercise oxygen consumption,(107) and improves with exercise training including in older HF patients.(74;108) Although most studies involved outpatients with stable HF, the 6MWD is safe, feasible and

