12.2 Secondary Efficacy Parameter

The secondary outcome for assessing the efficacy of the REHAB-HF intervention will be the total number of all-cause rehospitalizations during the 6 months following discharge from the index hospitalization.

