14.1 Statistical Methods

The primary aim of the study is to assess the efficacy of the REHAB-HF intervention on physical function measured by the total SPPB score. The effect of the intervention on SPPB score measured 3 months post-randomization will be estimated and tested for significance using analysis of covariance, where the randomized arm is the between-subject grouping variable and the pre-randomized measure of SPPB score, clinical site, age, gender, and ejection fraction category (preserved vs. reduced) will be covariates. Least square means will be used to estimate the intervention effect. Tests will be conducted at the 5% two-sided level of significance.

The secondary aim of the study is to assess the intervention's effect on the total number of all-cause rehospitalizations during the 6 months following discharge from the index hospitalization. Since the count of all-cause rehospitalizations per participant may not be normally distributed, the effect of the intervention on total all-cause rehospitalizations will be estimated using a Poisson model for modeling count data, where the randomized arm is the between-subject grouping variable and clinical site, age, gender, and ejection fraction category will be covariates. A supplemental analysis will be performed adding the duration of the index hospitalization and the number of inpatient intervention sessions as additional covariates.

The proportion of the intervention's effect on total all-cause rehospitalizations that can be explained by its effect on 3-month SPPB score will be analyzed by multivariable regression between total number of all-cause rehospitalizations and the residual of the analysis of covariance model for 3-month SPPB omitting intervention from the model.

Similar statistical methods as described above will be used for all of the exploratory efficacy parameters.

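### The share of the rehospitalization benefit credited to 3-month SPPB uses a count that starts 12 weeks before the SPPB is measured, so reverse effect can pass as mediation

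*Combined protocol and SAP*

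**What the plan says.** Section 2.3, item 2, sets the objective: "To estimate the proportion of the reduction in rehospitalizations explained by" the intervention's effect on the SPPB score. Section 14.1 gives the method as a "multivariable regression between total number of all-cause rehospitalizations and the residual of the analysis of covariance model for 3-month SPPB", with the intervention left out of that covariance model.

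The outcome is defined in Section 12.2 as "the total number of all-cause rehospitalizations during the 6 months following discharge from the index hospitalization". Section 9.1 schedules the SPPB visit at "12 weeks ± 10 days (unless intervention is extended, see section 7.3) from the day of discharge". Section 7.3 adds that for a participant with an acute illness, and likewise for one "hospitalized within 2 weeks of the anticipated date of the final 3-month visit, the visit will be delayed for up to 2 weeks"; the same delay applies in the control arm.

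Three other places bear on the reading. Section 3 points to "hospital processes, including forced bed rest which can markedly accelerate physical dysfunction". Section 7.2.1 says the intervention "begins during the acute hospitalization and continues for 12 weeks after discharge". Section 10.1.1 lists, among eight reasons for choosing the SPPB, that "in our pilot study, the improvement in SPPB explained 90% of the improvement in rehospitalizations, providing a mechanistic link".

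No section limits this analysis to events after the SPPB or adjusts it for earlier ones. SPPB is also measured at 1 month, and rehospitalizations at 1 and 3 months are exploratory endpoints, but neither is tied to this analysis.

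**The concern.** For SPPB to explain a reduction in rehospitalizations, the change in SPPB has to come before the events it is said to prevent. Here a large part of the count has accrued before the SPPB is taken. A patient readmitted in week 5 contributes to the outcome and may also walk more slowly at week 12 because of that stay. If the intervention prevents early readmissions by any route, part of that effect is then credited to SPPB. The reverse path follows from the protocol's own premise that hospital stays harm function.

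What is at stake is the interpretation of a numbered objective. Since the pilot's 90% is already presented as mechanistic, the trial's figure is likely to be read the same way. A reader could not tell whether better function prevented readmissions or fewer readmissions preserved function.

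**Working it through.** **The plan's own figure.** The only share explained in the document is the pilot's 90%. It cannot be reproduced, because no pilot patient data or model coefficients are given.

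**Window share.** Visit and count both start at index discharge (9.1, 12.2). Taking 6 months as 182 days:

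- nominal visit: 84/182 = 46%
- visit window: 74/182 = 41% to 94/182 = 52%
- 2-week delay: 98/182 = 54%

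This is a share of time, not of events; the plan does not give event timing. Section 14.1 times the SPPB from randomization instead of discharge, which shifts these figures only slightly.

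**Inputs for the bias (14.2).** SPPB mean square error 3.269; SPPB difference 0.63 (design) or 1.13 (pilot); 25% reduction, 0.41 absolute, so control rate 0.41/0.25 = 1.64.

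**Assumed.** SPPB loss b per early rehospitalization; constant hazard; no SPPB recovery by the visit; Poisson model with arm; share = 1 − adjusted/unadjusted log rate ratio. Section 14.1 does not fix the model form for this analysis.

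**By hand.** Suppose SPPB has no effect on rehospitalization. With early fraction f, the within-arm slope of the log rate on SPPB is then about −b·f/3.269, so

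false share ≈ (b × f × SPPB difference) / (3.269 × |ln 0.75|).

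For b = 0.5: 0.5 × 0.4615 × 0.63 / (3.269 × 0.2877) = 0.155. For b = 0.25 and 1.0 the results are 0.077 and 0.309. Simulation with 1 to 2 million patients per scenario gives 0.076, 0.156 and 0.305.

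**Sensitivity (simulated, true share zero).**

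| Scenario | loss 0.25 | loss 0.5 | loss 1.0 |
|---|---|---|---|
| Base case | 8% | 16% | 31% |
| Linear model with arm | 8% | 16% | 31% |
| No arm term (3% at zero loss) | 10% | 18% | 33% |
| Visit 10 days early | 7% | 14% | 27% |
| Visit 14 days late | 9% | 18% | 36% |
| SPPB recovery, 4-week half-life | 3% | 7% | 13% |
| 60% of events before week 12 | 10% | 20% | 40% |
| Patient heterogeneity (gamma variance 0.25) | 11% | 21% | 41% |
| SPPB difference 1.13 | 14% | 27% | 55% |

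In the base case, zero loss gives 0%. Bias can also go down: a true share of 50% with no loss and 30% measurement noise appears as 35%.

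**Time-ordered alternative.** Counting only events after the visit and adjusting for the earlier count gives about 0% at every loss when the true share is zero. Without the earlier count, a false share remains if patients differ in underlying risk: 3%, 6%, 11% at gamma variance 0.25, and 6%, 12%, 22% at 0.5.

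When the true share is 50% without noise, the version with the count gives 43% to 44% at no loss and 31% to 43% at losses of 0.25 to 1.0. The planned method gives 49% to 50% and 55% to 83%.

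**Precision.** At 0.85 × 360 = 306 patients, loss 0.5, true share 50% and no heterogeneity, the central 95% ranges of the proportion are:

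- planned: 0.25 to 1.65
- later events: 0.10 to 2.62
- later events with the earlier count: −1.47 to 2.44

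At gamma variance 0.25 they widen to 0.20 to 2.23, 0.10 to 2.90 and −2.31 to 3.92. The lower limit for later events depends on the scenario: a separate run without heterogeneity gave 0.09 to 2.19 if the SPPB loss itself raises later risk, and −0.67 to 2.79 if it does not.

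**The case against.** The analysis serves an item under Other Objectives and controls no decision. The size of the bias is wholly assumed, since the plan gives neither an SPPB loss per rehospitalization nor the timing of events. The largest figures need each early stay to cost, with no recovery, the 1.0 unit that Section 14.2 calls substantial. The bed-rest sentence in Section 3 is about the index decompensation, so applying it to later stays is an inference. The visit delay in Section 7.3 gives some patients time to recover before testing, and recovery more than halves the bias. Some early association may be genuine, because treatment starts in hospital. The alternative is imprecise, and since the earlier count is itself affected by arm, adjusting for it removes genuine early benefit.

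Most of this stands as a limit on size and reach, and it is why the point is not critical. It does not remove the flaw. The order of outcome and mediator is fixed by the plan's own schedule, and Section 3 also says that functional deficits persist. Section 10.1.1 shows that a causal reading is intended. The imprecision of the alternative applies to the planned proportion too, and argues for leading with an indirect effect on the log-rate scale.

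**Conclusion.** The concern holds. As written, the analysis can report the effect of early rehospitalization on SPPB as if it were the effect of SPPB on rehospitalization, and the planned figure cannot separate the two. The 46% follows directly from the plan. The false shares of 8%, 16% and 31% are illustrations under assumed losses, constant hazard and no recovery; the scenarios above with a non-zero loss run from 3% to 55%. The direction of the net error is not certain, because measurement noise pulls the estimate down. The plan should be changed on this point; the primary and secondary tests stand as they are.

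**What to change.** Keep the planned estimate and describe it as an association, not as causal mediation. Add one pre-specified sensitivity analysis:

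- Outcome: rehospitalizations from the 3-month visit to 6 months, with an offset for time at risk.
- Terms: 3-month SPPB, arm, the baseline covariates, and the number of rehospitalizations before the visit.
- Also show the version without the earlier count, noting that it stays confounded if patients differ in underlying risk.
- Report the indirect effect on the log-rate scale, with a bootstrap interval, beside any proportion.
- Optional: 1-month SPPB with events after that visit.

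Make no mechanistic claim from the planned figure alone, and do not treat agreement between the analyses as confirmation.

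The cost is SAP wording and a little programming; the data are already collected. The downsides should be stated:

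- Fewer events: the arm difference after week 12 is about 0.41 × 14/26 = 0.22 per patient under constant hazard, or 0.41 × 0.40 = 0.16 if 60% of events come earlier (assumed).
- A narrower estimand that drops genuine early benefit and can understate a true share: with 30% measurement noise, a true 50% appears as 17% to 32% when the earlier count is included.
- Coverage only of patients alive and seen at 3 months; Section 14.2 assumes 85% retention.

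### The planned share of the rehospitalization effect explained by SPPB rests on a slope that randomization does not protect, so part of any association from shared causes would be reported as mediation

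*Combined protocol and SAP*

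**What the plan says.** Other Objective 2 (section 2.3) is "To estimate the proportion of the reduction in rehospitalizations explained by" the change that the intervention produces in SPPB. Section 14.1 gives the method in one sentence: the proportion "will be analyzed by multivariable regression between total number of all-cause rehospitalizations and the residual of the analysis of covariance model"; in full, the regressor is the "residual of the analysis of covariance model for 3-month SPPB omitting intervention from the model". Besides baseline SPPB, the analysis of covariance has these terms: "clinical site, age, gender, and ejection fraction category (preserved vs. reduced) will be covariates".

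The plan calls the second regression multivariable but does not list its covariates or say whether arm is among them. It gives no formula or interval for the proportion, no assumption about confounding of SPPB and rehospitalization, and no sensitivity analysis.

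Two other places bear on the point. Section 3 says of comorbidities that "these contribute to impaired physical function(50) and subsequent adverse outcomes", and says of the authors' own model that "we have identified 5 factors that contribute to severely impaired physical function and subsequent events in older ADHF patients". The five are aging, HF disease, deconditioning, comorbidities and iatrogenesis. Section 10.1.1 lists among its reasons for choosing SPPB that "in our pilot study, the improvement in SPPB explained 90% of the improvement in rehospitalizations, providing a mechanistic link".

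**The concern.** Randomization makes the arms comparable, so the effect of arm on SPPB and the effect of arm on rehospitalizations are each protected. A proportion explained needs a third quantity: how the rehospitalization rate varies with SPPB among patients in the same arm. That slope is observational. A sicker patient may score low at 3 months and also be readmitted more often, with neither causing the other. Whatever slope this produces is multiplied by the intervention's effect on SPPB and counted as explained.

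Of the five factors in section 3, age is adjusted directly. Ejection fraction category and baseline SPPB pick up part of HF disease and deconditioning. Comorbidities and iatrogenesis have no named covariate.

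At stake is the interpretation. The pilot's figure is already described as mechanistic, and the trial's own estimate is likely to be read the same way. A confidence interval for the proportion would not reveal this bias, because it covers sampling error only.

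**Working it through.** **1. The plan's own figures (section 14.2).** The pilot SPPB effect of 1.13 is 17.9% of the control mean, so that mean is 1.13/0.179 = 6.313 and a 10% difference is 0.631. With residual variance 3.269, two-sided 5% and 80% power (squared sum of normal quantiles 7.849), n per arm = 2 × 7.849 × 3.269 / 0.631² = 128.8, so 129 per arm and 258 in total, as stated. 258/0.85 = 303.5, so 304, as stated. The variance and the effect can therefore be used here. The residual SD is √3.269 = 1.808.

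**2. How strong a shared cause the plan's numbers allow.** The secondary outcome needs 334 evaluable, or 167 per arm, for a difference of 0.41, which is 25% of 1.64 (so 1.64 against 1.23). With plain Poisson variance, n per arm = 7.849 × (1.64 + 1.23) / 0.41² = 134.0. The ratio 167/134.0 = 1.25 is the implied variance-to-mean ratio. Other readings of the inputs give 1.22 to 1.27.

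Let U be an unadjusted shared cause, normally distributed, with rehospitalization rate ratio R per SD. It alone gives a variance-to-mean ratio of 1 + mean × (exp((ln R)²) − 1). At the average mean of 1.435:

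- R = 1.45 gives 1.21.
- R = 1.5 gives 1.26.
- R = 2.0 gives 1.89.

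So R of about 1.45-1.5 is the most that fits, if U is the only source of extra-Poisson variation.

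**3. False share when SPPB carries nothing.** Take the proportion as 1 minus the ratio of the arm coefficient with the SPPB residual to that without it, both on the log-rate scale. The plan gives no formula, so this is an assumption. If U explains a fraction k of residual SPPB variance, then

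false share = a × √k × ln R / (1.808 × |ln RR|),

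where a is the SPPB effect and RR the rehospitalization rate ratio for arm. At the design effects (a = 0.63, RR = 0.75) the multiplier a/(1.808 × |ln RR|) is 1.211. At the pilot effects (a = 1.13, RR = 1.157/1.673 = 0.692) it is 1.695. The documents do not give k. The range 5-30% is assumed, as is 1.2 for the low end of R.

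| k | R | Design effects | Pilot effects |
|---|---|---|---|
| 5% | 1.2 | 4.9% | 6.9% |
| 10% | 1.5 | 15.5% | 21.7% |
| 20% | 1.5 | 22.0% | 30.7% |
| 30% | 1.5 | 26.9% | 37.6% |

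**4. Simulation check.** With 306 participants (360 × 0.85), arm in the count model and no causal SPPB effect, 600 trials per scenario gave 15.5% and 21.5% for the second and third rows at the design effects, and 20.5% and 30% at the pilot effects. Control runs behaved as they should. No shared cause returned 0%, and true 50% mediation with no shared cause returned 50%. In a stronger case (k = 20%, R = 2.0, pilot effects), adjusting for U cut a false 53% to 0.2%. The bias therefore comes from the omitted cause.

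**5. What a partial proxy buys.** If a baseline measure captures half of the variance of U, the false share is multiplied by 0.5/(1 − 0.5k). With k = 20% that is 0.556, so 22.0% falls to 12.2%.

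**The case against.** **The plan estimates; it does not test.** It states no null hypothesis and no significance test for mediation. A reader might infer an inflated false-positive rate, because the SPPB residual is often significant when a shared cause is present. The documents define no such test. Nor is significance the reported quantity: in a run where the intervention did not move SPPB, the residual was significant in 99.8% of trials while the proportion was 0%. The concern is bias in the estimated proportion, and it arises only if the intervention changes SPPB, as the trial expects.

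**Arm might be omitted from the count model.** A reader might take this from section 14.1. The wording removes the intervention only from the model that produces the residual. Omission from the second regression is one reading of an unlisted model, and a share of the arm effect needs an arm effect from some model.

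**The second regression might carry more covariates.** It might, since it is called multivariable. None is specified, so the point holds for the covariates that the plan names.

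**The pilot's 90% might be an artefact.** The documents do not support this inference. They give no pilot slope or formula, so the 90% cannot be recomputed. Working back, it needs 0.9 × ln(0.692)/1.13 = −0.294 on the log-rate scale per SPPB point. Producing that from a shared cause alone would require a variance-to-mean ratio of about 1.47, even if U were all of the residual SPPB variance. That is above the 1.22-1.27 implied by 334.

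**This is a general limit of mediation analysis, in a low-ranked objective.** Both parts are true, and both limit the weight of the point. They do not remove it, because the correction is cheap and section 10.1.1 already attaches causal language to the pilot's version of this quantity.

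**Conclusion.** The concern holds in a limited form. Followed with the covariates it names, section 14.1 would report part of the association between sickness, low function and readmission as mediation. With true mediation at zero, the false share is roughly 5-27% at the design effects and 7-38% at the pilot effects.

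The range rests on four assumptions: a shared cause accounting for 5-30% of residual SPPB variance; a rate ratio of 1.2 to about 1.5 per SD; the upper limit taken from a dispersion inferred from 334 rather than stated; and a proportion computed from the change in the arm coefficient. With no remaining shared cause the bias is zero. If counts are more dispersed than 334 implies, a stronger shared cause becomes possible.

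The primary SPPB comparison and the secondary rehospitalization comparison are unaffected.

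**What to change.** In section 14.1, replace the sentence on the proportion explained with a full specification:

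- The rehospitalization model includes randomized arm, the current covariates, and prespecified baseline severity measures already collected under Table 2 and section 10.5: 6MWD, handgrip, KCCQ, NT-proBNP, GDS-15 and MoCA. Add baseline comorbidity if it is recorded; Table 2 lists no comorbidity measure.
- The 3-month SPPB model carries the same baseline terms.
- The formula for the proportion is stated, and the estimate is reported with an interval.
- A sensitivity analysis recomputes the proportion over a stated range of unmeasured-confounder strength, expressed as association with SPPB and rate ratio for rehospitalization.
- The result is described as an association consistent with mediation, not as a demonstrated mechanism.

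The cost is SAP wording and analysis code, with no new data. The reported proportion will probably be smaller and less precise. Residual confounding will remain, because the added covariates are partial proxies; the sensitivity analysis is therefore needed as well as the adjustment.
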